### 1.2.8 Human Experience with HER2 Therapeutic Vaccines

The clinical efficacy of trastuzumab-based anti-HER2 passive immunotherapy and other HER2-targeted therapy has led to the development of vaccination strategies against HER2 that would ideally result in strong immunity producing immune memory associated with anti-tumor activity as well as prevention of tumor recurrence. Different anti-HER2 vaccine strategies currently

under investigation and in various stages of clinical development include DNA, peptide, whole tumor cell, and dendritic cell vaccines and combinations of the same e.g. peptide-loaded DC vaccines. Peptide vaccines have included monovalent and as well as polyvalent HER2 peptides and been associated with the development of humoral as well as cellular immune responses. We believe the use of our proposed AdHER2 DC vaccine will induce polyclonal antibody responses directed towards both the extracellular (EC) and transmembrane (TM) components of HER2 as well as potentially the intracellular domain (IC) as a result of epitope spreading. The multiple, unique HER2 epitopes targeted by this autologous vaccine platform are likely to differ from trastuzumab binding epitopes and may result in greater affinity and clinical activity than that seen with trastuzumab, especially in patients with lower levels of HER2 expression i.e. <3+ by IHC. In addition, based on our pre-clinical data, the anti-HER2 antibodies induced by vaccination appear to have functional activity that, unlike trastuzumab, is Fc receptor independent and that interfere with HER2 expression and phosphorylation. Hence, vaccine-induced anti-HER2 antibodies may also have clinically relevant anti-tumor activity in patients with resistance to trastuzumab, lapatinib or other HER2-directed therapies.

#### 1.2.9 Previous Human Experience with an Extracellular/Transmembrane/Intracellular HER2/neu Vaccine

Our collaborator [name], and his colleagues at the Karolinska Institute in Sweden have conducted a pilot clinical trial of a plasmid DNA human HER2/neu vaccine encoding the extracellular (EC), transmembrane (TM) and mutated intracellular (ICmutated) domains (ECTMICmutated) given with GM-CSF and IL-2. As a safety measure, a two base pair mutation was introduced in the IC domain to remove an autophosphorylation site that confers oncogenicity and maximize safety. The vaccine was administered to a total of eight patients and no clinical issues of acute toxicity, autoimmunity or cardio toxicity were identified. As might be expected with a DNA plasmid construct, the vaccine demonstrated limited immunogenicity: no specific T-cell proliferation following *in vitro* stimulation of *ex vivo* PBMCs with recombinant human HER2 protein was induced by vaccination. In fact, immediately following three complete cycles of vaccination, no or even decreased HER2-specific CD4+ T-cell responses were observed, but a significant increase in MHC class II restricted HER2-T-cell responses was detected at long term follow-up. Because concurrent trastuzumab therapy was permitted during the study,  $\lambda$ -subclass specific ELISAs were performed to measure endogenous antibody production without trastuzumab interference. Importantly, in a subgroup of patients, HER2-pDNA vaccination induced and boosted HER2-specific antibodies that could be detected for several years following the last vaccine administration.

We propose to carry out this phase I and pilot study of vaccination with AdHER2 transduced autologous dendritic cells in patients with 1+ to 3+ HER2neu expressing tumors. Part I involves vaccine dose escalation in a population with no prior exposure to trastuzumab or other HER2-directed agents to determine if there is a significant, adverse safety signal regarding cardiac toxicity, in addition to preliminary assessment of the vaccine's immunogenicity and clinical activity. Five doses of 5, 10, 20 or 40  $\times 10^6$  viable cells/AdHER2 vaccine will be given intradermally at Weeks 0, 4, 8, 16 and 24 in patients with metastatic solid tumors and adjuvant bladder cancer patients characterized by some HER2/neu expression. ***While these patients may be less likely to respond due to lower expression levels of the HER2 target, it is equally possible that they may respond better because they will have less peripheral tolerance to HER2.*** In addition, AdHER2 DC vaccination is likely to induce a polyclonal antibody response

to multiple HER2 epitopes that differ from the EC epitope targeted by trastuzumab. These differing polyclonal, multiple-epitope responses may be associated with anti-tumor activity. Once preliminary cardiac safety is demonstrated, Part II of the study will repeat the vaccine dose escalation *in a population with prior exposure to trastuzumab and other HER2 directed therapies* (as required by the FDA) to again determine whether there is an adverse safety signal regarding cardiac toxicity, in addition to assessment of the vaccine's immunogenicity and clinical activity. Vaccine dose escalation, administration and re-staging assessment is identical to that conducted in Part I.

#### 1.2.10.2 JPT Peptide Technologies, Midissia Therapeutics and NCI

A major objective of this study is to determine the immunogenicity of the AdHER2 DC vaccine. Specifically, we seek to examine whether AdHER2 DC vaccination is associated with a 3-fold increase in anti-HER2/neu antibody concentration (measured as mcg/mL) or a 4-fold increase in antibody dilution titers over baseline. Overlapping HER2 peptide microarrays will also be utilized to characterize both vaccine-induced anti-HER2 antibody and cellular responses.

Anti-HER2 cellular response and clinical response relationship with anti-Ad5 Ab.

#### 1.2.10.3 Anti-HER2 Cellular Response

The [name] lab, through support from the NCI Frederick Clinical Support Laboratory will assess vaccine-induced HER2-specific responses as measured by IFN- $\gamma$ , Granzyme A and Granzyme B ELISPOT assay and/or intracellular cytokine staining (ICS). The [name] lab, through support from the NCI Frederick Clinical Support Laboratory will check humoral immunity i.e. anti-Ad5 antibody titers at baseline as well as post vaccination, to determine if autologous AdHER2 DC vaccination results in a change in these anti-Ad5 titers over time, or is correlated with the increases in anti-HER2 antibody titers post vaccination.

#### 1.2.10.4 Circulating Tumor Cells (CTCs): [name], DTB, CCR, NCI

Analysis will be performed by the [name] laboratory utilizing ferrofluidic enrichment and multiparameter flow cytometric detection to study CTCs from a broad range of cancer types. CTCs will be identified as viable, nucleated cells, that positively express one or more epithelial or tumor markers and are negative for expression of hematopoietic markers. CTCs will be further characterized for markers for ICD such as calreticulin, Hsp70 and Hsp90.

#### 1.2.10.5 Immune cell subsets: [name], DTB, CCR, NCI

Peripheral blood mononuclear cells (PBMC) will be isolated from patient blood before and after treatment, labeled with a unique 2D barcode and viably stored. It will be thawed and assessed using multiparameter flow cytometry for immune subsets including but not necessarily limited to Tregs, myeloid-derived suppressor cells (MDSC), NK, NKT, CD4+ and CD8+ T-cells, and CD14+ monocyte subsets. Assessment will include functional markers, i.e. PD-1, Tim-3, CTLA-4, CD40, HLA-DR and PD-L1.

#### 1.2.10.6 Function-Associated mRNAs in Whole Blood: [name], Hitachi Chemical

Although there have been major recent advances in the field of cancer immunotherapy with the approval of sipuleucel-T (Provenge®) and ipilimumab (YERVOY™), a significant challenge that remains is identification of immunologic responses that correlate with beneficial clinical outcomes such as tumor regression or survival. In collaboration with [name] of Hitachi chemical, we will seek to explore whether characterization of a patient's baseline immune status using assessment of functional mRNAs can be utilized to predict who will respond to vaccination.

The assay is a novel high throughput real time PCR system for quantitatively assaying mRNA for any gene that is activated in cells. Specifically, the methodology allows for quantification of 17 different leukocyte-function-associated mRNAs in whole blood after *ex vivo* stimulation with up to 8 different antigens (e.g. rIL2, PHA, Anti-TCR, HER2, heat aggregated IgG (HAG, immune complex to activate Fc receptor), LPS, Zymosan, and PBS control) on pre-manufactured strips. Since the volume blood needed for this test is very small and cell isolation and culture are not necessary, this exploratory methodology may serve as a model of personalized medical diagnostics for patient-specific cancer vaccine immunotherapy.

## 2 ELIGIBILITY ASSESSMENT AND ENROLLMENT

### 2.1 ELIGIBILITY CRITERIA

#### 2.1.1 Common Eligibility for Parts I and II

- 2.1.1.1 Adults  $\geq 18$  with malignant soft tissue and bone tumors and recurrent or progressive, metastatic solid tumors who have progressed on standard therapies except in adjuvant for high risk bladder cancer in Part I.
- 2.1.1.2 Recurrent or progressive disease on prior standard therapies with known clinical benefit with the exception of adjuvant bladder cancer population.
- 2.1.1.3 Performance Status: ECOG 0-1. (Refer to [Appendix 1](#))
- 2.1.1.4 Baseline LVEF by 2D Echocardiogram  $\geq 53\%$ .
- 2.1.1.5 Greater than or equal to 1 week since standard or investigational treatment for metastatic disease.
- 2.1.1.6 Stable, concurrent use of hormone therapy for hormone receptor positive breast cancer is permitted.

2.1.1.7 Hematologic parameters: ANC  $\geq$  1000 cells/mm^3, ALC  $\geq$  300 cells/mm^3, Hemoglobin  $\geq$  9.0 gm/dL, WBC  $\geq$  2,500 cells/mm^3, platelet count  $\geq$  75,000/mm^3, PT/PTT  $\leq$  1.5X the upper limits of normal.

2.1.1.8 Chemistry parameters: Creatinine  $\leq$  1.5 mg/dL, SGOT and SGPT  $\leq$  3X the upper limits of normal and total bilirubin  $\leq$  1.5 mg/dL, Alk PO4  $\leq$  3X the upper limits of normal (except for patients with documented metastatic disease to bone and/or liver).

2.1.1.9 Negative serum beta HCG if female and of childbearing potential.

2.1.1.10 Negative HIV 1/2 serology and sample drawn for HTLV. Patients with HIV are excluded from participating on this clinical trial because their immunodeficiency would confound the evaluation of adverse events which would hinder meeting the primary objective.

2.1.1.11 Negative serology for hepatitis B and C unless the result is consistent with prior vaccination or prior infection with full recovery.

2.1.1.12 Willingness of female and male subjects to use effective contraception e.g. oral contraceptives, barrier device, intrauterine device, or condoms, during the study and for three months following the last dose of study vaccine. We suggest that subjects do not become pregnant or father a child during the study, and for 3 months following receipt of the investigational AdHER2 DC vaccine.

2.1.1.13 Able to understand and provide Informed Consent.

2.1.1.14 Patients with 1+ to 3+ HER2/neu expression by IHC or an equivocal or positive FISH result by 2013 ASCO/CAP guideline.

HER2 Detection Method	Negative	Equivocal	Positive
Vysis FISH Ratio (Measures HER2 oncogene)	-Single-probe average HER2 copy number $<4.0$ signals/cell -Dual-probe HER2/CEP17 ratio $<2.0$ with an average HER2 copy number $<4.0$ signals/cell	-Single-probe ISH average HER2 copy number $\geq 4.0$ and $<6.0$ signals/cell -Dual-probe HER2/CEP17 ratio $<2.0$ with an average HER2 copy number $\geq 4.0$ and $<6.0$ signals/cell	-Single-probe average HER2 copy number $\geq 6.0$ signals/cell -Dual-probe HER2/CEP17 ratio $\geq 2.0$ with an average HER2 copy number $<4.0$ signals per cell -Dual-probe HER2/CEP17 ratio $\geq 2.0$ with an average HER2 copy number $<4.0$ signals/cell -Dual-probe HER2/CEP17 ratio $<2.0$ with an average HER2 copy number $\geq 6.0$ signals/cell
IHC (Measures HER2 protein)	0-1+	2+	3+

2.1.1.15 Patients must have measurable disease, per RECIST 1.1. See Section [6.2](#) for the evaluation of measurable disease except adjuvant high risk bladder cancer.

## 2.1.2 Part I Eligibility

2.1.2.1 Naïve to trastuzumab (HerceptinTM), pertuzumab (PerjetaTM) and lapatinib (TykerbTM), ado-trastuzumab emtansine (KadcylaTM) or other HER2-directed therapies.

### 2.1.2.2 Malignancy as follows:

- Malignant soft tissue and bone tumors and recurrent or progressive, metastatic solid tumors who have progressed on standard therapies; or,
- Bladder cancer in the adjuvant setting (adjuvant bladder cancer patients):
  - Tumor stage T3a, T3b, T4a, T4b and any node positive disease regardless of tumor stage.
  - Status-post primary cystectomy with curative intent.
  - May or may not have received neoadjuvant cisplatin-based combination chemotherapy per NCCN guidelines.
  - May or may not have received adjuvant radiotherapy or chemotherapy based on pathologic risk per NCCN guidelines.
  - Greater than or equal to 6 weeks s/p primary surgery with curative intent.
- NOTE: Patients with breast, ovarian, cervical, colon, gastric/gastroesophageal junction, non-small cell lung, renal cell, bladder, malignant soft tissue and bone tumor, prostate cancer or other solid tumors.

## 2.1.3 Part II Eligibility

2.1.3.1 Malignant soft tissue and bone tumors and recurrent or progressive, metastatic solid tumors who have progressed on standard therapies.

2.1.3.2 Recurrent or progressive metastatic disease after standard of care HER2-targeted therapies; i.e. trastuzumab (HerceptinTM), pertuzumab (PerjetaTM), lapatinib (TykerbTM), ado-trastuzumab emtansine (TDM1) (KadcylaTM) or other HER2-directed therapies.

2.1.3.3 Stable, concurrent use of tamoxifen or aromatase inhibitors for hormone receptor positive breast cancer is permitted.

## 2.2 EXCLUSION CRITERIA

2.2.1.1 Pregnant women are excluded from this study because AdHER DC vaccine may have the potential for teratogenic or abortifacient effects. Because there is an unknown but potential risk for adverse events in nursing infants secondary to treatment of the mother with AdHER DC vaccine, breastfeeding should be discontinued if the mother is treated with AdHER DC vaccine.

2.2.1.2 Patients with active CNS metastases or leptomeningeal involvement by tumor (patients with a history of brain metastases who have successfully treated for brain metastasis by surgery or radiation and who have not had any evidence of the new or progressive CNS disease for more than 12 months are eligible).

2.2.1.3 Patients with rapidly progressing disease in the opinion of the Principal Investigator.

2.2.1.4 Patients with inadequate bilateral peripheral venous or central venous catheter access for the required apheresis to allow generation of the autologous AdHER2 DC vaccine product.

- 2.2.1.5 Clinically significant cardiac dysfunction defined as a history of  $\geq$  NYHA Class II symptoms, angina, congestive heart failure, myocardial infarction, arrhythmias or cardiac dysfunction requiring treatment or discontinuation of chemotherapy.
- 2.2.1.6 History of changes in baseline LVEF that occurred during prior treatment with anti-HER2 treatment.
- 2.2.1.7 Cumulative doxorubicin dose  $\geq 400\text{mg}/\text{m}^2$  ( $>450\text{ mg}/\text{m}^2$  for malignant soft tissue and bone tumor patients) or cumulative epirubicin dose  $\geq 800\text{mg}/\text{m}^2$ .
- 2.2.1.8 Use of any standard chemotherapy or other investigational agent(s) within 1 week of study enrollment.
- 2.2.1.9 Use of systemic corticosteroid therapy within 2 weeks of study enrollment, including patients receiving replacement corticosteroid therapy. Note: only topical, inhaled and intranasal steroid therapy is permitted.
- 2.2.1.10 Active systemic viral, bacterial or fungal infection requiring treatment.
- 2.2.1.11 A medical history which the treating physician believes causes the patient to be excluded. This includes a remote history of cancer. Please note: squamous cell carcinoma, basal cell carcinoma and remote history of cancer with no evidence of recurrence for the past 5 years are eligible.

## 2.2.2 Recruitment Strategies

This protocol is being conducted in collaboration with [name] of JPT Peptide Technologies as well as [name] of the University of Cincinnati, who was also significantly involved in the pre-clinical animal model studies of the AdHER2 vaccine platform before he left the NCI. We anticipate that a significant number of HER2 positive patients will be referred from these colleagues in addition to patients identified through affiliates at Walter Reed National Military Medical Center. We will submit approved protocol to [name] Research Foundation's Army of Women Program ([www.armyofwomen.org/](http://www.armyofwomen.org/)) and ResearchMatch (<https://www.researchmatch.org>) for review to allow contact with and recruitment through their volunteers. We also made contact with Office of Patient Recruitment, National Institutes of Health Clinical Center to update our contact information, generate materials including flyers, posting for social media and posters. Additionally, this study will be posted on NIH websites and on NIH social media forums. NCI Vaccine Branch Clinical Trials team also opened a twitter account (@NCICCR\_VB) for the patient recruitment and sharing the updated information on cancer vaccine and related topics with other professionals and general public. This account is officially registered to Office of Communications and Public Liaison at NCI.

In addition to the standard electronic mailings and postings by the NCI CCR Office of Patient Outreach and Recruitment, the former Principal Investigator, now a special volunteer at Vaccine Branch, CCR, NCI, [name] developed a brief video (no more than 5 minutes in length) that provides an informational overview to both patients and health care providers describing the scientific rationale for and design of the clinical study.

This video was posted to the YouTube channels of the NCI Office of Communications and the NIH Clinical Center. Given that so much of consumer media information is now provided in video format that can easily be accessed via the web using computers and smart phone operating systems and applications platforms, we believe that this could serve as a novel recruitment tool

for patients interested in participating in clinical research studies. See **Appendix 13**: Patient Recruitment Materials.

## **2.3 PRE-SCREENING AND SCREENING EVALUATION**

### **2.3.1 Pre-Screening**

All potential patients must provide written documentation of the HER2 status of their primary tumor and/or a recent tumor biopsy specimen, along with availability of a paraffin tissue block. For those with incomplete HER2 characterization as defined by the IHC or FISH, HER2 characterization will be performed by the NCI Laboratory of Pathology.

### **2.3.2 Screening Evaluation**

Patients will undergo a medical history and physical examination, review of concomitant medications, including review of symptoms, performance status, and life expectancy and apheresis clinic access assessment at screening. History will also specifically document:

- Prior exposure to anthracycline chemotherapy agents and total cumulative dose.
- Prior exposure to HER2-directed therapies: agent, duration and number of rounds of treatment.
- Documentation of New York Heart Association (NYHA) functional classification. (Refer to **Appendix 2**)
- Imaging studies (obtained within 30 days prior to enrollment). Note: if the patient had scans at an outside institution the patient will not be required a screening scan to consent. Instead, the baseline scan will be performed at NIH prior to treatment and used to identify target lesions.
  - CT scan of neck (optional), chest, abdomen and pelvis
  - MRI of the brain (in select clinically indicated patients)
  - Technetium 99 bone scan (if clinically indicated, for patients with bone metastases)
- 2D Echocardiogram with documentation of LVEF (obtained within 30 days prior to enrollment). Note: if the patient had an echo at an outside institution the patient will not be required a screening echo to consent. Instead, the baseline echo will be performed at NIH prior to treatment)
- Urinalysis
- Laboratory evaluation (obtained within 30 days prior to enrollment)
- CBC with differential counts, PT/PTT, acute care panel, hepatic panel, serum beta-HCG (for females with childbearing potential only), anti-HIV-1/2 Ab, anti-HCV Ab, HBsAg, HBs Ab, anti-HTLV-1/2 Ab, anti-CMV IgG/IgM and RPR

Refer to Section **3.4** for the Study Calendar schedule of on study clinical, laboratory, radiographic and research evaluations.

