## **2.5 BASELINE EVALUATION**

Below studies will be obtained within 30 days prior to the administration of the first dose of vaccine. If any of the studies were performed on another protocol, they may not need to be repeated.

- CBC with Differential
- Acute care panel, hepatic panel, mineral panel, total protein, amylase, lipase, uric acid
- PT/PTT
- Lipid panel
- Immunoglobulin quantification, IgE
- LDH
- CPK, Troponin I
- Thyroid screen (TSH, Free T4)
- 25-OH-vitamin D
- Lymphocyte subsets
- Tumor markers (optional)
- Urinalysis
- ABO typing and HLA A, B, C and DR (if not done in NIH Clinical Center in the past)
- CT CAP (to be done only if screening scans were performed at an outside institution and not repeated at the NCI).
- MRI Brain (to be done only if clinically indicated and screening scans were performed at an outside institution and not repeated at the NCI).
- CT Neck (to be done only if clinically indicated and screening scans were performed at an outside institution and not repeated at the NCI).
- Bone Scan (to be done only if patient has bone metastasis and screening scans were performed at an outside institution and not repeated at the NCI).
- Echocardiogram (to be done only if screening echo(s) were performed at an outside institution and not repeated at the NCI).

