 Clinical labs CBC with differential, PT/PTT, acute care panel, hepatic panel, mineral panel, total protein, amylase/lipase, uric acid, lipid panel.

 Tumor markers are optional and will be tested dependent on the primary sites. Patients with primary breast, ovarian and GI tract cancer might be tested for CA 125, CA 15-3, CA19-9, CA 27-29, and CEA. Other organ specific tumor markers can be tested

 Only until 12 weeks after the last dose of vaccination.

 Research bloods will not be used in data analysis if the patient has started on any treatment that can affect the data of the study. Week 40 and after samples will only be collected if the patient has not progressed (PD).

 This is optional and to be performed if clinically indicated. If the patient received scans within 30 days of enrollment at an outside institution the patient will not be required to have a second scan performed. Instead, the baseline scan will be used to collect target lesions.

 If the patient received scans within 30 days of enrollment at an outside institution the patient will not be required a screening scan to consent. Instead, the baseline scan will be used to identify target lesions. If the patient has bone metastasis and clinically indicated, a bone scan will be done at restaging.

 If the patient received scans within 30 days of enrollment at an outside institution the patient will not be required to have a second scan performed. Instead, the baseline scan will be used to collect target lesions. If a confirmatory scan is performed in less than 8 weeks from prior CT, the interval of CT follow-up will be adjusted to maintain 8 weeks interval to avoid unnecessary radiation exposure. For bladder cancer adjuvant indication, CT scans every 12 weeks during first 12 month, every 16 weeks for the next 12 months and at the end of study if no recurrence.

 Optional documentation on cardiac function will be collected once a patient is on study but off treatment for the purposes of long-term assessment of the impact of AdHER2 vaccination on cardiac function. Note: if the patient had an echo within 30 days of enrollment at an outside institution the patient will not be required a screening echo to consent. Instead, the baseline echo will be performed at NIH prior to treatment and used to identify target lesions.

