## **4 CONCOMITANT MEDICATIONS/MEASURES**

- Patients are allowed to be on concomitant therapy with tamoxifen or aromatase inhibitors for ER+ tumor status.
- Patients may be on concomitant drugs to prevent skeletal related events (SRE), including bisphosphonates and denosumab.
- Study subjects will be allowed to take multivitamins, analgesics (NSAIDS or acetaminophen), antipyretics, and antihistamines for symptomatic relief of local or systemic injection site reactions.
- Patients are allowed to continue on medications as clinically indicated for treatment of chronic medical conditions e.g. hypertension, diabetes, hypercholesterolemia, etc.
- Excluded Therapy:
  - Trastuzumab, pertuzumab, lapatinib, ado-trastuzumab emtansine (TDM1) or other HER2-directed therapies *within 1 week* of study enrollment.
  - Chemotherapy: Concomitant use of chemotherapy is not allowed during this trial.
  - Anti-Cancer Radionuclides: Concomitant use of anti-cancer radionuclides is not allowed during this trial. Patients will be allowed to co-enroll in studies of novel radionuclide imaging agents e.g. Indium CHX-A DTPA trastuzumab.
  - Secondary Hormonal Therapies: Concomitant use of supplementary hormonal treatments other than tamoxifen or aromatase inhibitors is not allowed.
  - Corticosteroids: Concomitant, chronic systemic corticosteroids are not allowed during this trial (excepting emergent use for clinical indications). However, the use

of inhaled corticosteroids, intranasal sprays and topical creams on limited body areas is allowed.

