#### 6.2.3 Methods for Evaluation of Measurable Disease

All measurements should be taken and recorded in metric notation using a ruler or calipers. All baseline evaluations should be performed as closely as possible to the beginning of treatment and never more than 4 weeks before the beginning of the treatment.

The same method of assessment and the same technique should be used to characterize each identified and reported lesion at baseline and during follow-up. Imaging-based evaluation is preferred to evaluation by clinical examination unless the lesion(s) being followed cannot be imaged but are assessable by clinical exam.

**Conventional CT and MRI:** This guideline has defined measurability of lesions on CT scan based on the assumption that CT slice thickness is 5 mm or less. If CT scans have slice thickness greater than 5 mm, the minimum size for a measurable lesion should be twice the slice thickness. For certain body parts or lesions, MRI can replace CT for response evaluation and such an MRI should be optimized for the evaluation of the type and site of the disease.

**Clinical lesions:** Clinically visible skin lesions will be utilized to evaluate measurable disease.

**Chest x-ray:** Chest x-ray will not be utilized to evaluate measurable disease.

**Ultrasound:** Ultrasound will not be utilized as a method of measurement.

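### For patients screened at NIH, the reference echo can precede the last prior anticancer dose and the baseline scan can be older than the protocol's own 4-week limit

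*Combined protocol and SAP*

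**What the plan says.** **Screening (2.3.2).** The echo entry reads "2D Echocardiogram with documentation of LVEF (obtained within 30 days prior to enrollment"; the scan entry reads "Imaging studies (obtained within 30 days prior to enrollment". Both count back from enrolment. If either was done outside, a new baseline study is to be done at NIH before treatment.

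**Baseline (2.5).** The section opens with a different anchor: "Below studies will be obtained within 30 days prior to the administration of the first dose of vaccine". Its echo line is then conditional: "Echocardiogram (to be done only if screening echo(s) were performed at an outside institution and not repeated at the NCI". The CT line carries the same condition. Studies done under another protocol may also be accepted without repeating.

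**On-study echoes (3.4, 3.5.2.3).** The first is at Week 4. There is none at Week 0.

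**Prior therapy.** Section 2.1.1.5 requires "Greater than or equal to 1 week since standard or investigational treatment for metastatic disease". Section 2.2.1.8 sets the same week for chemotherapy and investigational agents, and section 4 excludes HER2-directed agents "or other HER2-directed therapies *within 1 week* of study enrollment". All three end at or near enrolment, not at first vaccine.

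**Tumour baseline (6.2.3).** Baseline evaluations are to be "never more than 4 weeks before the beginning of the treatment".

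**Outside scans (3.4, footnote 14).** For a patient with a recent outside scan, "the patient will not be required to have a second scan performed".

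**The concern.** The main safety event, CTRCD, is a fall in LVEF from a baseline value (3.1.1: more than 10 points, to below 53%). It is interpretable only if nothing cardiotoxic happens between the reference echo and the first vaccine except what the reference already reflects. The protocol takes care over this after vaccination: 3.1.1 censors cardiac deterioration linked to later cardiotoxic drugs, and 3.5.3.7 takes such patients off study. No comparable rule covers the interval between the reference echo and Week 0.

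The cardiac limits are small: 2 of 6 at a dose level, 2 of 12 in the Part I expansion, 3 patients in Part II. One event caused by an earlier drug could affect a dose decision. The entry requirement of LVEF at least 53% (2.1.1.4) is also weakened if it is checked before the last potentially cardiotoxic dose.

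For the tumour objectives, an old scan charges growth before the first vaccine to the vaccine, in the fraction with stable disease or better. The scan windows also conflict with each other, whatever the size of that effect.

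**Working it through.** The documents give no figure for the age of the baseline studies, so there is none to reproduce. The check is day-counting on the protocol's own windows.

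**Inputs**
- Screening window W = 30 days before enrolment (2.3.2), or 30 days before first vaccine (2.5).
- Washout = 7 days before enrolment (2.1.1.5, 2.2.1.8, section 4).
- Scan limit = 28 days before treatment (6.2.3).
- L = days from enrolment to first vaccine. Apheresis is scheduled after eligibility and consent (3.1), and culture runs from Day 0 to Day 4 (Appendix 4). Four days is therefore a floor. No maximum is stated; the range 4 to 28 days is an assumption.

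**Formulas, for a patient screened at NIH**
- Under the 2.3.2 window: echo before last prior dose = 30 − 7 = 23 days at most; scan age at first vaccine = 30 + L.
- Under the 2.5 window: echo before last prior dose = 30 − (7 + L), not below 0; scan age = 30.
- Earliest NIH scan that still meets 6.2.3 = 28 − L days before enrolment.

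| L (days) | Echo precedes last dose, 2.3.2 | Echo precedes last dose, 2.5 | Scan age, 2.3.2 | Scan age, 2.5 | Scan meets 6.2.3 if no earlier than (days before enrolment) |
|---|---|---|---|---|---|
| 4 | 23 | 19 | 34 (6 over) | 30 (2 over) | 24 |
| 14 | 23 | 9 | 44 (16 over) | 30 (2 over) | 14 |
| 23 | 23 | 0 | 53 (25 over) | 30 (2 over) | 5 |
| 28 | 23 | 0 | 58 (30 over) | 30 (2 over) | 0 |

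A case that meets both 2.3.2 and 2.5: L = 4, echo 26 days before enrolment (30 before first vaccine), last prior dose about 7 days before enrolment (11 before first vaccine). The echo is 30 − 11 = 19 days older than that dose.

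**How sensitive the limits are to one event (conditional illustration only)**

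The protocol's 4.9% for 2 or more of 12 at a true rate of 3% reproduces: 1 − 0.97^12 − 12 × 0.03 × 0.97^11 = 0.049. If one of the 12 already counts because of an earlier drug, the chance of reaching the limit is 1 − 0.97^11 = 0.285. For 2 or more of 6, the figure is 1 − 0.97^6 − 6 × 0.03 × 0.97^5 = 0.012, and with one event given, 1 − 0.97^5 = 0.141. These figures take the carry-over event as having happened. They say nothing about how likely it is.

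**The case against.** **Section 2.5 has a first-dose window.** This is the strongest reply, and it stands in part. A reader might infer that an echo 30 days before enrolment followed by a drug 8 days before enrolment satisfies every rule. It does not: with at least 4 days to first vaccine, that echo is at least 34 days old and outside 2.5. The window shrinks the echo problem and closes it once L reaches 23 days. It does not close it for shorter lags, and at 30 days it still exceeds the 28-day scan limit. The conditional wording in 2.5 also leaves unclear whether the window applies to an NIH study that is not repeated.

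**The group is narrow.** Patients with an outside echo get a new NIH echo before treatment. Registration follows consent within 24 hours (2.4), so an NIH study well before enrolment would usually come from another protocol or from care. Recruitment leans on outside referral (2.2.2). This is fair on frequency, although 2.5 expressly allows studies from another protocol to be reused.

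**There are other safeguards.** Rapid progression, prior LVEF change on anti-HER2 treatment, significant cardiac history and high cumulative anthracycline dose are exclusions (2.2). Section 3.5.3.6 removes patients who progress rapidly between screening and baseline. A qualifying LVEF fall needs a cardiac consultation (3.1.1). So it is too strong to say that every such fall would be counted against the vaccine. But consultation cannot recover a reference value that was not measured, and an NIH-screened patient has no separate baseline scan on which imaging could show progression.

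**The probabilities prove little.** Agreed. The 2-of-12 limit applies to Part I, whose patients are naive to HER2-directed therapy, so carry-over there could come only from other drugs. A reader might take 14% or 28% as the expected error rate; the documents do not support that.

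**Footnote 14 may only be loose.** Its following sentence says the baseline scan is used for target lesions. Read with footnote 13 and 2.3.2, it may waive only a second screening scan. It is ambiguous rather than flatly contradictory.

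**Conclusion.** The point holds for patients screened at NIH. Their reference LVEF and entry check can precede the last prior anticancer dose by up to about 23 days under 2.3.2. Under 2.5 the gap is 19 days at a 4-day lag, falling to none from 23 days. Their baseline scan can exceed the limit in 6.2.3 by at least 6 days under 2.3.2 and by 2 days under 2.5, so the scan windows conflict on either reading.

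The result rests on two things: 4 days as the shortest time from enrolment to vaccine, and an NIH screening study serving as baseline without repetition, as 2.5 states.

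Two larger conclusions do not follow. The documents do not show that all baselines run from enrolment, because outside echoes are redone and 2.5 has its own window. Nor do they show a bias of known size in the toxicity or response rates, because they give no frequency for such gaps or for LVEF falls from a preceding drug. The case for change is an internal conflict and an avoidable weakness in the reference for a primary endpoint, both cheap to remove.

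**What to change.** In 2.3.2 and 2.5, anchor both baselines to the first vaccine:
- **Baseline LVEF**, used for the entry check and as the CTRCD reference: an NIH echo done after the last dose of prior anticancer therapy and within 30 days before the first vaccine.
- **Baseline scan:** done after the last prior therapy and within 4 weeks before the first vaccine, as 6.2.3 already states.
- Time the single planned echo and scan to meet these windows, and repeat one only if it falls outside.
- Reconcile 2.3.2, 2.5, 6.2.3 and study calendar footnotes 12 to 14, and state whether an outside scan can serve as baseline.

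The cost is amendment wording, later scheduling of studies already planned, and an occasional repeat when apheresis or manufacture is delayed. With a 14-day lag, for example, an NIH scan more than 14 days before enrolment would need repeating.

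The change does not remove late cardiac effects of earlier drugs: an echo soon after the last dose may not yet show them. It removes only the part of the problem that comes from measuring the reference too early.
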